4.3 Contraception

Tabelecleucel and pembrolizumab may have adverse effects on a fetus in utero. Furthermore, it is not known if these investigational products have transient adverse effects on the composition of sperm.

Females of childbearing potential and males with a female partner of childbearing potential must be willing to use a highly effective method of contraception.

In order to participate in the study, subjects of childbearing potential must adhere to the contraception requirement (described above) from the day of investigational product initiation (or 14 days prior to the initiation of investigational product for oral contraception) throughout the study period up to 120 days after the last dose of investigational product. If there is any question that a subject of childbearing potential will not reliably comply with the requirements for contraception, that subject should not be entered into the study.

4.4 Nursing Women

It is unknown whether tabelecleucel and pembrolizumab is excreted in human milk. Since many drugs are excreted in human milk, and because of the potential for serious adverse reactions in the nursing infant, subjects who are breastfeeding are not eligible for enrollment.

4.5 Meals and Dietary Restrictions

Subjects should maintain a normal diet unless modifications are required to manage an adverse event (AE) such as diarrhea, nausea or vomiting.

4.6 Subject Withdrawal Criteria

A subject may withdraw either from (1) investigational product treatment only, in which case the subject will continue protocol defined follow-up assessments or (2) study participation, in which case investigational product and study assessments will be discontinued. Whenever possible, continue protocol-defined follow-up after the subject has discontinued investigational product treatment (refer to Section [6.7](#)).

Investigational product treatment may be discontinued for any of the following reasons:

- Occurrence of an AE that precludes further treatment, refer to Section [5.2.5](#)
- Achieves a sustained CR, refer to Section [5.2.4](#)
- Receives a prohibited treatment, such as use of a different investigational product or non-protocol anti-NPC therapy
- Decision (by subject or investigator) that continued investigational product treatment is not in the subject's best interest

Study participation may be discontinued for any of the following reasons:

- Withdrawal of consent by subject or subject's legally authorized representative
- Early closure of the study by the sponsor
- Subject is lost to follow-up

4.7 Subject Replacement

Subjects who discontinue due to a DLT after receiving both pembrolizumab and tabelecleucel during the 21-day DLT assessment window will not be replaced; however, subjects who discontinue due to a DLT associated with the first infusion of pembrolizumab (ie, prior to any tabelecleucel infusion) will be replaced. Subjects who discontinue from Cohort 1 for any reason other than a DLT prior to completing the 21-day DLT assessment window will be replaced until the required number of evaluable subjects complete the 21-day DLT assessment window. Subjects will not be replaced in Cohort 2.

5 TREATMENT WITH INVESTIGATIONAL PRODUCT

5.1 Description of Investigational Products

The treatments to be used in this study are outlined below in [Table 4](#).

Table 4 Investigational Products					
Investigational Product Name	Dosage Formulation	Unit Dose Strength(s)	Dosage Level(s)	Route of Administration	Sourcing
Pembrolizumab	Solution for infusion	100 mg/vial	200 mg Q3W (adults, \geq 18 years) 2 mg/kg Q3W (children, 12 to $<$ 18 years)	IV infusion	Merck
Tabelecleucel	Sterile aqueous suspension	Up to 5×10^7 cells/mL	1 or 2×10^6 cells/kg	IV infusion	Atara

5.1.1 Formulation

Tabelecleucel is formulated as a sterile aqueous suspension intended for IV administration. The product contains 10% dimethyl sulfoxide, 15% human serum albumin, and buffered saline.

Pembrolizumab is provided as a sterile solution of 100 mg in 4 mL (25 mg/mL).

Refer to the Investigational Product Manual for details of dose preparation.

5.1.2 Packaging and Labeling

Tabelecleucel is supplied in single-use vials.

Pembrolizumab is supplied in a single-use vial for IV infusion.

5.1.3 Storage and Handling

Tabelecleucel will be shipped to study sites where it will be stored in a liquid nitrogen-charged canister until ready for dose preparation. To prepare the product for infusion, the frozen vial is to be thawed and the dose prepared as specified in the Investigational Product Manual. Once thawed, the product must be used immediately; the unused portion must not be refrozen or reused and must be discarded. The thawed product is to be handled or transported at ambient room temperature.

Pembrolizumab should be stored refrigerated at 2° to 8°C (36° to 46°F) and should not be frozen or shaken. Protect from light.

Refer to the Investigational Product Manual for detailed instructions for storage and handling of the products.

5.2 Administration of Investigational Products

A treatment/consolidation cycle in the Treatment Phase of the study will last 3 weeks (21 days) and consist of 1 dose of pembrolizumab administered on Day 1 and 3 doses of tabelecleucel administered on Day 1, Day 8 (\pm 2), and Day 15 (\pm 2) of each cycle; pembrolizumab will be administered approximately 1 hour before tabelecleucel.

During the Maintenance Phase of the study, a maintenance cycle will last 84 days. Subjects will receive pembrolizumab on Day 1, Day 21 (\pm 2), Day 42 (\pm 2), and Day 63 (\pm 2) and tabelecleucel on Day 1 of each 84-day cycle; pembrolizumab will be administered approximately 1 hour before tabelecleucel.

Pembrolizumab: Pembrolizumab will be administered using IV infusion on Day 1 of the 21-day treatment/consolidation cycle after all procedures and assessments have been completed (except vital signs, which will be measured before and after all investigational product infusions).

Pembrolizumab will be administered as a dose of 200 mg (adults \geq 18 years of age) or 2 mg/kg (children 12 to $<$ 18 years of age) using a 30-minute IV infusion. Investigators should make every effort to target infusion timing to be as close to 30 minutes as possible. However, given the variability of infusion pumps from study site to site, a window between -5 minutes and +10 minutes is permitted, ie, infusion time is 30 minutes (-5 min/+10 min).

The Pharmacy Manual contains specific instructions for the preparation of the pembrolizumab infusion and administration of infusion solution.

Tabelecleucel: Tabelecleucel will be selected for each subject from the bank of available tabelecleucel cell products based on matching \geq 2 HLA alleles, at least one of which is a restricting HLA allele, shared between the tabelecleucel source material (donor) and the subject.

Tabelecleucel will be administered via a slow IV push over 5 to 10 minutes at a dose of 2×10^6 cells/kg body weight (the Cohort 1 de-escalation dose is 1.0×10^6 cells/kg) after all procedures and assessments have been completed (except vital signs, which will be measured before and after all investigational product infusions).

5.2.1 *Timing of Dose Administration*

On the study days in which both investigational products are administered (ie, Day 1 of treatment/consolidation cycles and Day 1 of maintenance cycles), tabelecleucel will be administered 1 hour (\pm 10 minutes) after the completion of pembrolizumab.

Note: Dosing interruptions are permitted in the case of medical/surgical events or logistical reasons (ie, elective surgery, unrelated medical events, subject vacation, holidays) not related to the administration of investigation product. Subjects should be placed back on the treatment schedule within 3 weeks of the scheduled interruption, unless otherwise discussed with the sponsor's medical monitor. The reason for dose interruption should be documented in the subject's study record.

5.2.2 *Duration of Treatment and Subject Participation*

The duration of treatment is dependent on a subject's response to treatment and is estimated to be approximately 2 years for subjects with a response to treatment (CR, PR, or SD): a maximum of 4 treatment/consolidation cycles (21-day cycles of 3 infusions of tabelecleucel and 1 of pembrolizumab) and maintenance cycles (84-day cycles of 4 infusions of pembrolizumab and

1 of tabelecleucel) until up to a total of 35 pembrolizumab infusions (including for treatment, consolidation, and maintenance) have been given.

After treatment/consolidation and maintenance cycles, subjects will have an End-of-Treatment visit (30 days after the last dose of investigational product) and then enter Quarterly Follow-up for 12 months after the last dose of investigational product. Before receiving any treatment, subjects must undergo a tabelecleucel inventory check and screening, with screening up to 28 days prior to the first dose of investigational product.

5.2.3 *Definition of Dose-limiting Toxicity*

All toxicities will be graded based on the investigator's assessment using CTCAE version 5, except for certain events described in Section 8.3, which have a separate grading system.

The DLT window of observation will be during Treatment Cycle 1 only (ie, during the first 21-day cycle; adverse events (AEs) meeting the definition of a DLT but occurring after this period will not be considered DLTs).

The occurrence of any of the following toxicities during Treatment Cycle 1 will be considered a DLT, if assessed by the investigator to be possibly related or related to investigational product administration (either tabelecleucel and/or pembrolizumab), excluding toxicities clearly not related to the investigational product, such as disease progression, environmental factors, unrelated trauma, etc.:

- Grade 4 nonhematologic toxicity (not laboratory).
- Grade 4 hematologic toxicity lasting ≥ 7 days, except thrombocytopenia:
 - Grade 4 thrombocytopenia of any duration
 - Grade 3 thrombocytopenia associated with bleeding that requires a platelet transfusion
- Any nonhematologic AE grade ≥ 3 in severity should be considered a DLT, with the following exceptions: grade 3 fatigue lasting ≤ 3 days; grade 3 diarrhea, nausea, or vomiting without use of anti-emetics or anti-diarrheals per standard of care; grade 3 rash without use of corticosteroids or anti-inflammatory agents per standard of care.
- Any grade 3 or grade 4 non-hematologic laboratory value if:
 - Clinically significant medical intervention is required to treat the subject, or
 - The abnormality leads to hospitalization, or
 - The abnormality persists for > 1 week.
 - The abnormality results in a Drug-induced Liver Injury (DILI)
 - Exceptions: Clinically nonsignificant, treatable, or reversible laboratory abnormalities including liver function tests, uric acid, etc.

- Febrile neutropenia grade 3 or grade 4:
 - Grade 3 is defined as ANC < 1000/mm³ with a single temperature of > 38.3 degrees C (101 degrees F) or a sustained temperature of ≥ 38 degrees C (100.4 degrees F) for more than 1 hour
 - Grade 4 is defined as ANC < 1000/mm³ with a single temperature of > 38.3 degrees C (101 degrees F) or a sustained temperature of ≥ 38 degrees C (100.4 degrees F) for more than 1 hour, with life-threatening consequences and urgent intervention indicated.
- Prolonged delay (> 2 weeks) in initiating Cycle 2 due to treatment-related toxicity.
- Any treatment-related toxicity that causes the subject to discontinue treatment during Cycle 1.
- Missing > 25% of pembrolizumab or tabelecleucel doses as a result of investigational product-related AE(s) during the first cycle.
- Grade 5 toxicity.

Any subject experiencing any DLT will be withdrawn from treatment (both investigational products). Whenever possible, protocol-defined follow-up will be continued after the subject has discontinued investigational product treatment (refer to Section 6.7).

MTD definition: The MTD is defined as the highest dose level at which the subject incidence of a DLTs during the first 21-day cycle of investigational product dosing is < 33%.

RP2D definition: The RP2D is no higher than the MTD and is based on optimal benefit-risk, as determined by the SDRC.

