5.2.5 Dose Modifications

5.2.5.1 Dose Modification and Toxicity Management for Immune-related AEs associated with Pembrolizumab

AEs associated with pembrolizumab exposure may represent an immunologic etiology. These immune-related AEs (irAEs) may occur shortly after the first dose or several months after the

last dose of pembrolizumab treatment and may affect more than one body system simultaneously. Therefore, early recognition and initiation of treatment is critical to reduce complications. Based on existing clinical study data, most irAEs were reversible and could be managed with interruptions of pembrolizumab, administration of corticosteroids and/or other supportive care. For suspected irAEs, ensure adequate evaluation to confirm etiology or exclude other causes. Additional procedures or tests such as bronchoscopy, endoscopy, skin biopsy may be included as part of the evaluation. Based on the severity of irAEs, withhold or permanently discontinue pembrolizumab and administer corticosteroids. Dose modification and toxicity management guidelines for irAEs associated with pembrolizumab are provided in [Table 5](#), and refer to the approved label. See Section [5.3.1.1](#) for supportive care guidelines, including use of corticosteroids.

Table 5 Dose Modification and Toxicity Management Guidelines for Immune-related Adverse Events Associated with Pembrolizumab

General instructions:				
irAEs	Toxicity grade or conditions	Action taken to pembrolizumab ^a	irAE management with corticosteroid and/or other therapies	Monitor and follow-up
Pneumonitis	Grade 2	Withhold	Administer corticosteroids (initial dose of 1-2 mg/kg prednisone or equivalent) followed by taper	Monitor subjects for signs and symptoms of pneumonitis Evaluate subjects with suspected pneumonitis with radiographic imaging and initiate corticosteroid treatment Add prophylactic antibiotics for opportunistic infections
	Grade 3 or 4, or recurrent Grade 2	Permanently discontinue		
Diarrhea / Colitis	Grade 2 or 3	Withhold		

irAEs	Toxicity grade or conditions	Action taken to pembrolizumab ^a	irAE management with corticosteroid and/or other therapies	Monitor and follow-up

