	Grade 4	Permanently discontinue	Administer corticosteroids (initial dose of 1-2 mg/kg prednisone or equivalent) followed by taper	Monitor subjects for signs and symptoms of enterocolitis (ie, diarrhea, abdominal pain, blood or mucus in stool with or without fever) and of bowel perforation (ie, peritoneal signs and ileus). Subjects with Grade \geq 2 diarrhea suspecting colitis should consider GI consultation and performing endoscopy to rule out colitis. Subjects with diarrhea/colitis should be advised to drink liberal quantities of clear fluids. If sufficient oral fluid intake is not feasible, fluid and electrolytes should be substituted via IV infusion.
AST / ALT elevation or Increased TBILI	Grade 2	Withhold	Administer corticosteroids (initial dose of 0.5-1 mg/kg prednisone or equivalent) followed by taper	Monitor with liver function tests (consider weekly or more frequently until liver enzyme value returned to baseline or is stable)
	Grade 3 or 4	Permanently discontinue	Administer corticosteroids (initial dose of 1-2 mg/kg prednisone or equivalent) followed by taper	
Type 1 diabetes mellitus (T1DM) or Hyperglycemia	Newly onset T1DM or Grade 3 or 4 hyperglycemia associated with evidence of β -cell failure	Withhold	Initiate insulin replacement therapy for subjects with T1DM Administer anti-hyperglycemic in subjects with hyperglycemia	Monitor subjects for hyperglycemia or other signs and symptoms of diabetes.
Hypophysitis	Grade 2	Withhold		

irAEs	Toxicity grade or conditions	Action taken to pembrolizumab ^a	irAE management with corticosteroid and/or other therapies	Monitor and follow-up
	Grade 3 or 4	Withhold or permanently discontinue	Administer corticosteroids and initiate hormonal replacements as clinically indicated.	Monitor for signs and symptoms of hypophysitis (including hypopituitarism and adrenal insufficiency)
Hyperthyroidism	Grade 2	Continue	Treat with non-selective beta-blockers (eg, propranolol) or thionamides as appropriate	Monitor for signs and symptoms of thyroid disorders.
	Grade 3 or 4	Withhold or permanently discontinue		
Hypothyroidism	Grade 2-4	Continue	Initiate thyroid replacement hormones (eg, levothyroxine or liothyroinine) per standard of care	Monitor for signs and symptoms of thyroid disorders.
Nephritis and Renal dysfunction	Grade 2	Withhold	Administer corticosteroids (prednisone 1-2 mg/kg or equivalent) followed by taper.	Monitor changes of renal function
	Grade 3 or 4	Permanently discontinue		

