5.2.5.3 Other Allowed Dose Interruption for Pembrolizumab

Pembrolizumab may be interrupted for situations other than treatment emergent related AEs such as medical / surgical events or logistical reasons not related to study therapy. Subjects should be placed back on study therapy within 3 weeks of the scheduled interruption, unless otherwise discussed with the sponsor's medical monitor. The reason for dose interruption should be documented in the subject's study record.

5.2.5.4 *Dose Modification for Tabelecleucel*

If ≥ 2 of the initial 6, or ≥ 4 of the initial 12 Cohort 1 subjects experience a DLT in the first 21 days, the dose of tabelecleucel will be reduced to 1×10^6 cells/kg/dose, and the subsequent 12 subjects will be treated with the combination of tabelecleucel at 1×10^6 cells/kg/dose and pembrolizumab at the recommended dose level. Otherwise, all 12 subjects in Cohort 1 will receive tabelecleucel at 2×10^6 cells/kg/dose and pembrolizumab at the recommended dose level. An SDRC composed of representatives from the sponsor and the principal investigators or designated sub-investigators from all sites enrolling subjects in Cohort 1 will review reported DLTs and cumulative safety data to determine further enrollment. The data review will occur as soon as possible after Cycle 1 Day 21 of the last subject in Cohort 1. For additional details on dose stopping rules (refer to Section 3.3 for additional details).

5.2.5.5 *Discontinuation of One Investigational Product*

Upon approval by the medical monitor, a subject may continue to receive 1 investigational product if the other is withheld or discontinued for any reason other than due to a DLT observed during the first 21 days of combination treatment.

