5.3 Prior and Concomitant Medications/Therapies

5.3.1 *Permitted Medications/Therapies*

All treatments that the investigator considers necessary for a subject's welfare may be administered at the discretion of the investigator in keeping with the community standards of medical care; however, refer to prohibited medications and therapies in Section 5.3.1.1. All concomitant medication will be recorded, including all prescription, over-the-counter, herbal supplements, and IV medications and fluids. If changes occur during the study period, documentation of drug dosage, frequency, route, and date should also be recorded.

The investigator or qualified designee will review prior medication use, including any protocol-specified washout requirement, and record prior medication taken by the subject within 30 days before the first dose of investigational product and 30 days after the last dose of investigational product should be recorded. Concomitant medications administered after 30 days after the last dose of investigational product should be recorded if related to any serious AEs (SAEs) and AEs of special interest as defined in Section 8.2.

5.3.1.1 *Rescue Medications and Supportive Care*

Subjects should receive appropriate supportive care measures as deemed necessary by the investigator. Suggested supportive care measures for the management of AEs with potential immunologic etiology are outlined along with the dose modification guidelines in Section 5.2.5 (Table 5). Where appropriate, these guidelines include the use of oral or intravenous treatment with corticosteroids, as well as additional anti-inflammatory agents if symptoms do not improve with administration of corticosteroids. Note that several courses of steroid tapering may be necessary as symptoms may worsen when the steroid dose is decreased. For each disorder, attempts should be made to rule out other causes such as metastatic disease or bacterial or viral

infection, which might require additional supportive care. The treatment guidelines are intended to be applied when the investigator determines the events to be related to pembrolizumab.

If a pembrolizumab-related toxicity requires > 0.5 mg/kg of prednisone equivalent, then tabelecleucel should be held until the steroids are tapered to below 0.5 mg/kg.

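### The grade 3 diarrhea exception in the DLT definition omits corticosteroids, unlike the rash exception beside it, so a few steroid-treated events could go uncounted (minor)

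*Protocol*

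**What the plan says.** The exceptions in Protocol 5.2.3 include "grade 3 diarrhea, nausea, or vomiting without use of anti-emetics or anti-diarrheals per standard of care; grade 3 rash without use of corticosteroids". The rash clause goes on to name anti-inflammatory agents; the diarrhea clause names no steroid.

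For immune-related diarrhea or colitis of grade 2 or 3, Table 5 (section 5.2.5.1) withholds pembrolizumab and says: "Administer corticosteroids (initial dose of 1-2 mg/kg prednisone or equivalent) followed by taper". The row mentions fluids but no anti-diarrheal. For suspected colitis at grade 2 or above, it adds that subjects "should consider GI consultation and performing endoscopy to rule out colitis".

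Other provisions bear on whether such an event is counted:

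- Section 5.3.1.1: "If a pembrolizumab-related toxicity requires > 0.5 mg/kg of prednisone equivalent, then tabelecleucel should be held".
- Section 5.2.3 also makes a DLT of missing more than 25% of either product's Cycle 1 doses because of a related AE, a treatment-related discontinuation in Cycle 1, and a toxicity-related delay of more than 2 weeks in starting Cycle 2.
- Section 5.2.5.5: "Upon approval by the medical monitor, a subject may continue to receive 1 investigational product if the other is withheld or discontinued", unless the reason is a DLT in the first 21 days.

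SAP 8.1.1 takes the DLT definition from Protocol 5.2.3 unchanged, and SAP 11.1 plans a DLT table.

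**The concern.** The drug class that the protocol prescribes for immune-related diarrhea is the one its diarrhea exception leaves out. The literal result is odd: grade 3 diarrhea that settles on an anti-diarrheal is a DLT, while grade 3 diarrhea serious enough for 1-2 mg/kg prednisone, with no anti-diarrheal, may not be. The phrase about standard of care can instead be read as exempting events that have not yet had adequate supportive care. On that reading too, diarrhea treated with steroids alone is exempt.

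DLT incidence is a primary endpoint and defines the MTD, with a limit of less than 33%. Under Protocol 3.5 one subject can change the outcome: 1 of 6 continues and 2 of 6 de-escalates; 3 of 12 = 25.0% proceeds and 4 of 12 = 33.3% does not.

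**Working it through.** The plan states no figure for this, so the check has two parts: a trace through the criteria, and an illustration under assumed rates.

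**1. Which events escape.** Take related grade 3 diarrhea treated with systemic steroids.

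- *Anti-diarrheal also used:* the exception is lost, so it is a DLT. Supportive care is the investigator's choice (5.3.1.1: "Subjects should receive appropriate supportive care measures as deemed necessary by the investigator").
- *Recorded as a diagnosis:* section 5.2.5.1 says "For suspected irAEs, ensure adequate evaluation to confirm etiology or exclude other causes", and 8.1.2 prefers a diagnosis to a symptom. Grade 3 colitis or GvHD is outside the exception, so it is a DLT.
- *Tabelecleucel dose missed:* by section 5.2, a cycle will "consist of 1 dose of pembrolizumab administered on Day 1 and 3 doses of tabelecleucel administered on Day 1", with the others on Days 8 and 15. One missed dose is 1/3 = 33.3%, above 25%, so it is a DLT.
- *Onset after the third dose (nominally Days 16-21):* no Cycle 1 dose remains, so the missed-dose rule cannot apply.
- *Earlier onset, no dose missed:* this can also escape. Steroids may stay at or below 0.5 mg/kg or be tapered below it in time, or the dose may still be given within its ±2-day window. The hold in 5.3.1.1 is also written only for pembrolizumab-related toxicity.
- *Cycle 1 discontinuation or late Cycle 2:* a DLT. Cycle 2 Day 1 is Day 22, and 22 + 14 = Day 36. Onset on Day 16 leaves 36 − 16 = 20 days; onset on Day 21 leaves 36 − 21 = 15.

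What escapes is an event recorded as diarrhea, given steroids without an anti-diarrheal, with no missed dose, no Cycle 1 discontinuation, and Cycle 2 started by Day 36.

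**2. Illustration for late onset only.** Assumptions, none from the documents: true DLT-type rate p; share s of those events being such diarrhea; onset even over 21 days; every event in the 6-day window escapes.

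- Uncounted rate: u = p × s × 6/21. Counted rate: p − u.
- Expected uncounted in 12 subjects: 12u. Chance of at least one: 1 − (1 − u)^12.
- De-escalation at 2×10^6 (section 3.5): P(at least 2 of 6) + P(at most 1 of 6 and at least 4 of 12), exact binomial.

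Worked case, p = 0.10 and s = 0.25: u = 0.10 × 0.25 × 6/21 = 0.0071; counted rate 0.0929; 12u = 0.086; chance of at least one 8.2%; de-escalation 12.1% → 10.5%.

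| p | s | Expected uncounted in 12 | Chance of ≥1 | De-escalation, all counted → some uncounted |
|---|---|---|---|---|
| 10% | 10% | 0.03 | 3.4% | 12.1% → 11.4% |
| 10% | 25% | 0.09 | 8.2% | 12.1% → 10.5% |
| 10% | 50% | 0.17 | 15.9% | 12.1% → 9.1% |
| 20% | 25% | 0.17 | 15.9% | 38.8% → 34.6% |
| 33% | 25% | 0.28 | 24.9% | 73.5% → 68.1% |
| 33% | 50% | 0.57 | 44.0% | 73.5% → 62.2% |

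The ±2-day dose window makes the period 4 to 8 days. For p = 10%, s = 25% that gives 0.06 to 0.11 events and de-escalation of 11.0% to 10.1%. If only half or a quarter of late events get past the other criteria (assumed), the same case gives 0.04 or 0.02 events and de-escalation of 11.3% or 11.7%.

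**3. Effect of one subject on the reported incidence.** Hypothetically, 0/12 becoming 1/12 moves the exact 95% interval from 0-26.5% to 0.2-38.5%.

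**The case against.** **Steroids may already count.** The protocol does not define anti-diarrheals, and an investigator could treat prednisone as standard care for immune-related diarrhea, which would end the exception. That is possible but strained, because the same sentence names corticosteroids separately for rash. Nor must the two lists match, since each may simply name the usual agents for its symptom. That explains the drafting but does not close the gap.

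**The Cycle 2 delay rule may catch nearly everything.** Early in treatment both products may be on hold, and only 15-20 days remain before the delay becomes a DLT. The general-instructions row of Table 5 has no text in the copy reviewed, and 5.2.5.1 also points to the approved label, so whether a taper fits cannot be judged. It is also unstated whether tabelecleucel alone, with medical monitor approval, counts as starting Cycle 2. If it does not, withholding pembrolizumab beyond Day 36 is itself a DLT. This objection stands: the documents do not show that any event would in fact escape.

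**Nothing is hidden.** SAP 11.1 lists all AEs and tabulates TEAEs by worst grade, and the Safety Data Review Committee sees cumulative safety data. The RP2D rests on benefit-risk, not on the count alone. SAP section 1 says the study ended in Phase 1B with 12 enrolled. All of this stands and keeps the point minor.

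**Conclusion.** The mismatch in 5.2.3 is real and the SAP carries it over, but the affected group is small. This is a minor point, to consider rather than to require. No event rate can be derived from the documents, and few or none are expected in 12 subjects.

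A reader might infer more than the documents support:

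- *That steroid-treated grade 3 diarrhea generally escapes.* It does not; most routes lead to a DLT by another criterion.
- *That the table gives upper bounds.* It does not. It covers late onset only, and earlier events with no missed dose can add to it. Against that, it assumes every late event escapes, which the other criteria make unlikely. The shares and even onset are assumptions.
- *That toxicity was concealed or Cohort 2 opened on an undercount.* Escaped events remain in the listings and the committee's data, and Cohort 2 was not enrolled. What is left is the accuracy of the reported DLT incidence.

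**What to change.** In 5.2.3, extend the agents whose use ends the exception for grade 3 diarrhea, nausea or vomiting to *anti-emetics, anti-diarrheals or systemic corticosteroids*. That is enough for parity with rash. A broader clause covering anything managed under Table 5 is not advised: it would force withdrawal from both products where Table 5 only withholds pembrolizumab at grade 3.

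For the 12 subjects already treated, keep the count under the current text as the reported DLT incidence, and add one descriptive line to the DLT table with the count under the amended wording. If the two agree, the line shows that the gap had no effect.

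Cost: one phrase and one table line. AE grade, dates, relatedness and concomitant medications are already collected. The downside applies to any prospective use: a subject newly classed as a DLT would be withdrawn from both products. For subjects already treated the second count is post hoc and descriptive only.
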